8.1.2. Exclusion Criteria

Patients will be excluded from study enrollment if they meet **any** of the following criteria:

- [8] are investigator site personnel directly affiliated with this study and their immediate families. Immediate family is defined as a spouse, parent, child, or sibling, whether biological or legally adopted.
- [9] are Lilly employees.
- [10] are currently enrolled in a clinical trial involving an investigational product or off-label use of a drug or device, or are concurrently enrolled in any other type of medical research judged not to be scientifically or medically compatible with this study.
- [11] have pustular, erythrodermic, and/or guttate forms of psoriasis.
- [12] have a history of drug-induced psoriasis.
- [13] had a clinically significant flare of psoriasis during the 12 weeks before baseline (Week 0; Visit 2).

[14] have received systemic nonbiologic psoriasis therapy (including but not limited to oral psoralens and ultraviolet A [PUVA] light therapy, cyclosporine, corticosteroids, methotrexate, oral retinoids, mycophenolate mofetil, thioguanine, hydroxyurea, sirolimus, azathioprine, fumaric acid derivatives, or 1, 25 dihydroxy vitamin D3 and analogues) or phototherapy (including either oral or topical PUVA light therapy, ultraviolet B, self-treatment with tanning beds, or therapeutic sunbathing) within 4 weeks prior to baseline (Week 0; Visit 2) or have had topical psoriasis treatment (including but not limited to corticosteroids, anthralin, calcipotriene, topical vitamin D derivatives, retinoids, tazarotene, emollients, and other nonprescription topical products containing urea, >3% salicylic acid, or α - or β -hydroxyl acids), or medicated shampoos [for example those that contain >3% salicylic acid, corticosteroids, coal tar, or vitamin D3 analogues]) within the previous 2 weeks prior to baseline (Week 0; Visit 2).

Exceptions: mild (for example, desonide) or least potent (for example, hydrocortisone) topical steroids will be permitted for use, limited to the face, axilla, and/or genitalia.

[15] cannot avoid excessive sun exposure or use of tanning booths for at least 4 weeks prior to baseline (Week 0; Visit 2) and during the study.

[16] current or recent use of any biologic agent within the following washout periods: etanercept <28 days; infliximab, adalimumab, or alefacept <60 days; golimumab <90 days; ustekinumab <8 months; rituximab or efalizumab <12 months; or any other biologic agent <5 half-lives prior to baseline (Week 0; Visit 2).

[17] have ever received natalizumab or other agents that target α -4-integrin.

[18] have previously completed or withdrawn from this study, participated in any other study with ixekizumab, or have participated in any study investigating other IL-17 antagonists.

[19] have a known allergy or hypersensitivity to any biologic therapy that would pose an unacceptable risk to the patient if participating in this study.

[20] have had a live vaccination within 12 weeks prior to baseline (Week 0; Visit 2), intend to have a live vaccination during the study or within 12 months of completing treatment in this study, or have participated in a vaccine clinical study within 12 weeks prior to baseline. Investigators should review the vaccination status of their patients and follow the local guidelines for adult vaccination with nonlive vaccines intended to prevent infectious disease prior to therapy.

(Note: Killed/inactive vaccines are expected to be safe.)

- [21] had a vaccination with Bacillus Calmette-Guérin (BCG) within 12 months prior to baseline (Week 0; Visit 2) or intend to have this vaccination with BCG during the study or within 12 months of completing treatment in this study.
- [22] had any major surgery within 8 weeks prior to baseline (Week 0; Visit 2) or will require such during the study that, in the opinion of the investigator in consultation with Lilly or its designee, would pose an unacceptable risk to the patient.
- [23] have current or a history of lymphoproliferative disease; or signs or symptoms of lymphoproliferative disease; or have active or history of malignant disease.
- (Note: Patients with successfully treated basal cell carcinoma [no more than 3 treatments for removal of basal cell carcinoma], squamous cell carcinoma of the skin, or cervical carcinoma in situ, with no evidence of recurrence within the 5 years prior to baseline [Week 0; Visit 2] may participate in the study.)
- [24] have the presence of significant uncontrolled cerebrocardiovascular disorder (for example, MI, unstable angina, unstable arterial hypertension, moderate to severe [New York Heart Association class III/IV] heart failure, or cerebrovascular accident); respiratory, hepatic, renal, gastrointestinal, endocrine, hematologic, neurologic, or neuropsychiatric disorder; or abnormal laboratory values at screening that, in the opinion of the investigator, pose an unacceptable risk to the patient if participating in the study or risk of interfering with the interpretation of data.
- [25] have had fluid overload, MI, or new-onset ischemic heart disease (for example, unstable angina), uncompensated heart failure or, in the opinion of the investigator, other serious cardiac disease within 12 weeks prior to baseline (Week 0; Visit 2).
- [26] have the presence of significant uncontrolled neuropsychiatric disorder, have history of a suicide attempt, have a score of 3 on Item 12 (Thoughts of Death or Suicide) of the 16-item Quick Inventory of Depressive Symptomatology–Self Report (QIDS-SR₁₆) at screening (Visit 1), or are clinically judged by the investigator to be at risk for suicide.
- [27] had a serious infection (for example, pneumonia, cellulitis), have been hospitalized, or have received intravenous (IV) antibiotics for an infection within 12 weeks prior to baseline (Week 0; Visit 2); had a serious bone or joint infection within 24 weeks prior to baseline; have ever had an infection of an artificial joint; or are immunocompromised to an extent such that participation in the study would pose an unacceptable risk to the patient.
- [28] have or have had an infection that is typical of an immunocompromised host and/or that occurs with increased incidence in an immunocompromised host (including, but not limited to, *Pneumocystis jirovecii* pneumonia, histoplasmosis, or coccidioidomycosis) or have a known immunodeficiency.

- [29] have a herpes zoster or any other clinically apparent varicella-zoster virus infection or had such within 12 weeks of baseline (Week 0; Visit 2).
- [30] have any other active or recent infection within 4 weeks of baseline (Week 0; Visit 2) that, in the opinion of the investigator, would pose an unacceptable risk to the patient if participating in the study; these patients may be rescreened (1 time) ≥ 4 weeks after documented resolution of symptoms.
- [31] have a body temperature $\geq 38^{\circ}\text{C}$ (100.5°F) at baseline (Week 0; Visit 2); these patients may be rescreened (1 time) ≥ 4 weeks after documented resolution of elevated temperature.
- [32] have clinical evidence or suspicion of active TB or have previously had evidence of active TB and did not receive appropriate and documented treatment. (Refer to Section 10.4.3.5 for additional details on determining full TB exclusion criteria.)
- a Evidence of active TB is documented by a positive purified protein derivative (PPD) test (≥ 5 -mm induration) which is to be read between 48 and 72 hours after placement, regardless of vaccination history, medical history, clinical symptoms, and abnormal chest x-ray at screening.
 - b If either the QuantiFERON[®]-TB Gold test (QTF) or T-SPOT[®] TB test (T-SPOT) is available, it may be used as an alternative instead of the PPD test, per principal investigator preference or judgment, and may be read locally. Locally read results must be documented in the eCRF.

have evidence of latent TB (as documented by a positive QTF or T-SPOT or PPD [≥ 5 -mm induration] with no clinical symptoms or signs consistent with active TB, and a normal chest x-ray at screening) **unless** patients complete at least 4 weeks of appropriate treatment prior to randomization and agree to complete the remainder of treatment while in the trial (see Section 10.4.3.5 for additional requirements).

- a If the QTF or T-SPOT test is indeterminate, the test may be repeated once within approximately 2 weeks of the initial value. If the repeat test is indeterminate, the patient will be excluded from the study. If the retest is positive with no clinical evidence of TB, the patient will be considered to have latent TB.
- b If the PPD test is performed and positive (≥ 5 -mm induration) and the patient has no medical history or chest x-ray findings consistent with active TB, a retest can be performed using a QTF or T-SPOT test.

Note: If retest is done with QTF or T-SPOT, this result will be used to determine eligibility in place of the PPD result. Indeterminate results of either test are to be handled as directed above.

- c Exceptions include patients with a history of active or latent TB who have documented evidence of appropriate treatment.

- [33] have uncontrolled arterial hypertension characterized by a systolic blood pressure (BP) >160 mm Hg or diastolic BP >100 mm Hg.
- (Note: This will be determined by 2 consecutive elevated readings. If an initial BP reading exceeds this limit, the BP may be repeated once after the patient has rested sitting for ≥10 minutes. If the repeat value is less than the criterion limits, the second value may be accepted.)
- [34] are positive for human immunodeficiency virus (HIV) serology (positive for HIV antibody).
- [35] have evidence of active hepatitis B virus (positive for hepatitis B surface antigen) OR are positive for hepatitis B core antibody and negative for hepatitis B surface antibody.
- [36] have evidence of or test positive for hepatitis C virus (HCV). A positive test for HCV is defined as: (1) positive for hepatitis C antibody and (2) positive via a confirmatory test for HCV (for example, HCV polymerase chain reaction).
- [37] have clinical laboratory test results at screening that are outside the normal reference range for the population and are considered clinically significant and/or have any of the following specific abnormalities:
- [37a] neutrophil count <1500 cells/μL (<1.50×10³ cells/μL or <1.50 GI/L)
 - [37b] lymphocyte count <500 cells/μL (<0.50×10³ cells/μL or <0.50 GI/L)
 - [37c] platelet count <100,000 cells/μL (<100×10³ cells/μL or <100 GI/L)
 - [37d] aspartate aminotransferase (AST) or alanine aminotransferase (ALT) >2.5 times the upper limit of normal (>2.5xULN)
 - [37e] total white blood cell (WBC) count <3000 cells/μL (<3.00×10³ cells/μL or <3.00 GI/L)
 - [37f] hemoglobin <8.5 g/dL (85.0 g/L) for male patients and <8.0 g/dL (80 g/L) for female patients
 - [37g] serum creatinine >2.0 mg/dL.
- (Note: The AST and ALT may be repeated once within a week if the initial response exceeds this limit, and the repeat value may be accepted if it meets this criterion. Other laboratory tests should not be repeated unless there is a technical error or clinical reasons to believe a result may be erroneous.)
- [38] have ECG abnormalities that are considered clinically significant and would pose an unacceptable risk to the patient if participating in the study.
- [39] have any other condition that precludes the patient from following and completing the protocol, in the opinion of the investigator.

- [40] have donated blood >400 mL within the last 4 weeks prior to baseline or intend to donate blood during the course of the study.
- [41] are women who are lactating or breastfeeding.
- [42] are unwilling to abstain from alcohol beverage intake 24 hours prior to any scheduled visits until the completion of all study visit procedures.
- [43] have used any traditional Chinese treatments within 14 days prior to study enrollment or intend to use any traditional Chinese treatment during the study.
- [44] Have allergy to rubber or latex.

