8.2.1.2. Discontinuations from Investigational Product or from the Study

In addition, patients will be discontinued from the investigational product or from the study in the following circumstances:

- Enrollment in any other clinical trial involving an investigational product or enrollment in any other type of medical research judged not to be scientifically or medically compatible with this study.
- Investigator decision:
 - The investigator decides that the patient should be discontinued from the study.
 - If the patient, for any reason, requires treatment with another therapeutic agent that has been demonstrated to be effective for treatment of the study indication, discontinuation from the study occurs prior to introduction of the other agent.
- Subject decision:
 - The patient requests to be discontinued from the study.
- Sponsor decision:
 - Lilly stops the study or stops the patient's participation in the study for medical, safety, regulatory, or other reasons consistent with applicable laws, regulations, and GCP.
- AE:
 - If a clinically significant event (CSE) occurs, the investigational product is to be discontinued and appropriate measures taken. Lilly or its designee should be alerted immediately. A CSE will be defined as a moderate to severe AE, abnormal clinical sign, or clinical laboratory finding that may pose a risk to the well-being of the subject. Refer to Section 10.4, Safety Evaluations.
 - A clinically significant systemic hypersensitivity reaction occurs following administration of the investigational product (for example, drug-related symptomatic bronchospasm, allergy-related edema/angioedema, or hypotension) and requires parenteral medication, does not respond to symptomatic medication, or results in clinical sequelae or an anaphylactic reaction.

After the investigator's determination that CSE criteria have been met and the investigator's judgment of relatedness to the investigational product is documented, a decision will be made between the investigator and Lilly or its designee regarding subject discontinuation.

The nature of any conditions, clinical signs or symptoms, or abnormal laboratory values present at the time of discontinuation and any applicable follow-up procedures will be documented.

Discontinuation procedures are outlined in the Study Schedules ([Attachment 1](#) and [Attachment 2](#)).

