10.4.3.5. Chest X-Ray and Tuberculosis Testing

A posterior-anterior view chest x-ray will be obtained, unless the x-ray or results from a chest x-ray obtained within 6 months prior to the study are available. The chest x-ray or results will be reviewed by the investigator or designee to exclude patients with active TB infection.

In addition, patients will be tested at screening as indicated in the Study Schedules ([Attachment 1](#) and [Attachment 2](#)) for evidence of active or latent TB (positive PPD [≥ 5 -mm induration] or positive QTF or T-SPOT at screening but no other evidence of active TB). In sites where the QTF or T-SPOT test is available and, in the judgment of the investigator, preferred as an alternative to the PPD skin test for the evaluation of TB infection, it may be used instead of the

PPD test (positive test excluded) and may be read locally. If the QTF or T-SPOT test is indeterminate, 1 retest is allowed. If the retest is indeterminate, the patient will be excluded from the study. If the retest is positive but without clinical evidence of TB, the patient will be considered as latent TB for study purposes.

Patients with documentation of a negative test result within 3 months prior to baseline (Week 0; Visit 2) do not need a TB screen at Visit 1. Documentation of this test result must include a record of the size of the induration response. A PPD test recorded as negative without documenting the size of induration will result in a retest.

However, patients with a positive QTF or T-SPOT at screening, but no other evidence of active TB, may be rescreened 1 time and may be enrolled without repeating the test if the following conditions are met:

- after receiving at least 4 weeks of appropriate latent TB infection (LTBI) therapy, and
- no evidence of hepatotoxicity (ALT/AST must remain $\leq 2 \times \text{ULN}$) upon retesting of serum ALT/AST prior to randomization (such patients must complete appropriate LTBI therapy during the course of the study in order to remain eligible), and
- meet all other inclusion and exclusion criteria for participation.

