If rescreening occurs within 6 months of the screening chest x-ray, there is no necessity for repeat of chest x-ray for considering enrollment. Patients who have a documented history of completing an appropriate TB treatment regimen with no history of re-exposure to TB since their treatment was completed and no evidence of active TB are eligible to participate in the study. Patients who have had household contact with a person with active TB are excluded, unless appropriate and documented prophylaxis for TB was given.

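### Exclusion [32] and Protocol Section 10.4.3.5 are not aligned on TB eligibility, and the cross-references in [32] do not fully settle the differences

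*Protocol*

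**What the plan says.** Protocol Section 8.1.2, criterion [32], has two limbs.

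- **Active TB.** Clinical evidence or suspicion of active TB excludes the patient. The reader is told: "Refer to Section 10.4.3.5 for additional details on determining full TB exclusion criteria".
- **Latent TB.** A positive QTF, T-SPOT or PPD with no sign of active disease and a normal chest x-ray excludes the patient, unless at least 4 weeks of treatment precede randomization and the patient agrees to finish the course. The limb adds "see Section 10.4.3.5 for additional requirements". Its item c reads: "Exceptions include patients with a history of active or latent TB who have documented evidence of appropriate treatment".

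Section 10.4.3.5 covers the same ground.

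- **Rescreen route.** "However, patients with a positive QTF or T-SPOT at screening, but no other evidence of active TB, may be rescreened 1 time". The conditions are at least 4 weeks of latent-TB therapy, ALT/AST no higher than 2×ULN on retest before randomization, and all other entry criteria. On continuing therapy it adds: "such patients must complete appropriate LTBI therapy during the course of the study in order to remain eligible".
- **Previously treated TB.** Patients with a documented, completed regimen, "with no history of re-exposure to TB since their treatment was completed and no evidence of active TB are eligible".
- **Household contact.** "Patients who have had household contact with a person with active TB are excluded, unless appropriate and documented prophylaxis for TB was given".

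Section 8.2.1.2 opens its list with "In addition, patients will be discontinued from the investigational product or from the study in the following circumstances". It then gives enrollment in other research, investigator, patient and sponsor decisions, and adverse events. It has no TB item and no reference to 10.4.3.5. Section 10.6 makes discontinuation for noncompliance optional.

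**The concern.** Section 8.1 permits no waivers of the entry criteria, so the text itself has to decide each case. Where two sections state different conditions for the same kind of patient, sites in a multicenter study can reach different answers in good faith.

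The rules involved guard against TB reactivation and liver toxicity. If patients on latent-TB therapy are admitted under different liver-enzyme limits depending on which TB test a site used, transaminase changes due to that therapy could also appear in the safety summaries of small dose groups.

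**Working it through.** No figure in the plan can be reproduced here. The check sets the clauses side by side and follows each cross-reference.

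**1. Previously treated TB**

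| Condition | [32] | 10.4.3.5 |
|---|---|---|
| Documented appropriate treatment | item c | yes, worded as a completed regimen |
| No active TB | opening of [32] | yes |
| No re-exposure since treatment | not stated | yes |

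Only re-exposure is truly missing from [32]. The cross-reference brings 10.4.3.5 into play but does not settle the point. Item c is worded as an exception to the exclusion and has no pointer of its own, while 10.4.3.5 says who is eligible and bars the re-exposed patient only by implication.

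The household-contact rule is also absent from the text of [32]. It is stated outright as an exclusion in 10.4.3.5 and [32] refers there, so it creates no conflict.

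**2. Latent TB found by PPD alone**

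Such a patient can exist. PPD is an accepted test, and [32] makes a QTF or T-SPOT retest after a positive PPD optional. If the retest is done, its result replaces the PPD, and a positive retest leads into the named route. The problem is therefore confined to PPD-positive patients who are not retested. Section 8.1 allows any screen failure one rescreen, so they can return after therapy.

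The text allows three readings:

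- **A.** [32] sends all three tests to 10.4.3.5, so the 2×ULN condition covers PPD.
- **B.** The condition covers only the tests it names. PPD patients then face [37d], together with the judgment-based laboratory exclusions in [24] and the lead text of [37].
- **C.** The 10.4.3.5 route is open only to the named tests, so a PPD-only patient has no way in.

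| ALT/AST | A | B | C |
|---|---|---|---|
| up to 2×ULN | may enter | may enter | no route |
| above 2, up to 2.5×ULN | excluded | may enter unless excluded on judgment | no route |
| above 2.5×ULN | excluded | excluded | no route |

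For a QTF- or T-SPOT-positive patient on this route, 10.4.3.5 is explicit that a value above 2×ULN fails. That is a stricter subgroup condition and does not contradict [37d].

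**3. Not completing latent-TB therapy**

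Section 10.4.3.5 makes completion a condition of remaining eligible. In 8.2.1.2 the only routes that could apply are investigator or sponsor decision, and 10.6 is permissive. The condition therefore has no stated consequence.

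The single-dose phase has one injection, so dosing can be affected only in the multiple-dose phase. From Attachment 2, the doses after Day 1 are:

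- Q2W: Days 15, 29, 43 and 57, which is 4 doses
- Q4W: Days 29 and 57, which is 2 doses

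These are the most that could still be scheduled when a patient stops therapy.

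**4. Scale of one patient**

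The completer target is 10 per regimen: 1/10 = 10%. The safety population is everyone dosed (SAP Section 8). With up to 30 enrolled and 1:1 randomization, 30/2 = 15 per regimen: 1/15 = 6.7%.

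**The case against.** The strongest reply is that [32] points to 10.4.3.5 twice, once for the full TB exclusion criteria and once for additional requirements, so a site following [32] must apply both. That stands. A reader might infer that the same patient is enrolled under one section and barred under the other. The documents do not support that, because the sections are meant to be read together. The cross-reference still leaves an exception worded without the re-exposure condition, and a liver-enzyme condition that names only two of the three tests.

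A reader might also infer that PPD-diagnosed patients are held only to 2.5×ULN. That goes too far. Criterion [24] and the lead text of [37] allow exclusion for abnormal laboratory values on judgment, and reading A would apply the 2×ULN condition to them. What can be said is that the text does not choose between the readings.

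On discontinuation, 8.2.1.2 never directs that a patient who stops latent-TB therapy stays on drug, and the investigator or the sponsor can stop treatment. This is an unlinked requirement, not a pair of opposing instructions.

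Finally, concomitant medication is listed by patient (SAP 9.6.2) and no inferential safety analysis is planned (SAP 9.6.9), so latent-TB therapy would be visible to anyone reading the safety data. That limits the harm to interpretation. It does not make enrollment consistent across sites.

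**Conclusion.** The point holds as a mismatch in eligibility text that should be corrected. Two differences survive the cross-references: the re-exposure condition for previously treated TB, and the scope of the ALT/AST condition when latent TB is found by PPD alone. The missing link between 10.4.3.5 and 8.2.1.2 is a lesser gap, relevant to dosing only in the multiple-dose phase.

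The patients affected are treated patients with later re-exposure, PPD-only patients (most visibly those above 2 and up to 2.5×ULN), and multiple-dose patients who stop latent-TB therapy. The documents do not say how many of any of these to expect, so the effect on the safety tables cannot be sized beyond the share of one patient, 6.7% to 10% of a regimen. The conclusion rests on PPD being used at some sites without a confirmatory retest, which the protocol allows. The sample size and the descriptive analyses are unaffected.

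**What to change.** Reconcile [32], 10.4.3.5 and 8.2.1.2 so that three things are each stated once and consistently:

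1. the conditions under which a patient with previously treated TB is eligible, including whether re-exposure matters;
2. which TB tests the ALT/AST condition covers, with an explicit statement for a patient found by PPD alone;
3. what follows if latent-TB therapy is not completed, with 8.2.1.2 and 10.4.3.5 agreeing.

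The sponsor decides which version stands; this review takes no position on the clinical rule. The cost is a few lines in an amendment or clarification letter. No new test is needed, because ALT and AST are already part of the screening chemistry.
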